7. NOTATION OF TREATMENT GROUPS AND VISITS

Notation of treatment groups

The following notation of **treatment groups** will be used throughout the report:

Full Notation (as used in the study protocol)	Notation Used Throughout All Tables, Listings, and Figures
Tapinarof Cream 1%, rolling over from DMVT-505-3101 or DMVT-505-3102	Tapinarof Cream 1% (Pivotal)
Vehicle Cream, rolling over from DMVT-505-3101 or DMVT-505-3102	Vehicle Cream (Pivotal)
Tapinarof Cream 1% and Vehicle Cream (Pivotal)	Total (Pivotal)
Tapinarof Cream 1%, rolling over from DMVT-505-2104	Tapinarof Cream 1% (2104)
Tapinarof Cream 1%, enrolling directly into DMVT-505-3103	Tapinarof Cream 1% (Direct-Enroll)
Tapinarof Cream 1%	Total (Overall)

Visit terminology

Visit	Notation Used Throughout All Tables, Listings, and Figures
Screening, Days -30 to Day -1, Visit V0	Screening
Baseline, Day 1, Visit V1	Baseline
Week 4, Day 29 (± 3 days), Visit V2	Week 4
Week 8, Day 57 (± 3 days), Visit V3	Week 8
Week 12, Day 85 (± 3 days), Visit V4	Week 12
Week 16, Day 113 (± 3 days), Visit V5	Week 16
Week 20, Day 141 (± 3 days), Visit V6	Week 20
Week 24, Day 169 (± 3 days), Visit V7	Week 24
Week 28, Day 197 (± 3 days), Visit V8	Week 28
Week 32, Day 225 (± 3 days), Visit V9	Week 32
Week 36, Day 253 (± 3 days), Visit V10	Week 36
Week 40, Day 281 (± 3 days), Visit V11	Week 40
Week 44, Day 309 (± 3 days), Visit V12	Week 44
Week 48, Day 337 (± 3 days), Visit V13 (End of Treatment)	Week 48
Week 49, Day 344 (± 3 days), Visit V14 (End of Study/Follow-up)	Week 49

Note: A phone call to review study drug application instructions, if applicable, and to record AEs and concomitant medication use will occur on Week 2, Day 15 (± 3 days).

Analysis visits

Study days are measured from baseline (Visit 1) in the extension study. Study days corresponding to measurements are calculated as:

- Assessment date – date of baseline (Visit 1) + 1 if assessment date is on or after the date of baseline (Visit 1)
- Assessment date – date of baseline (Visit 1) if assessment date is before the date of baseline (Visit 1)

Efficacy and safety endpoints will be summarized according to the nominal visit as assigned by the investigator except for assessments collected on early termination visits. Early termination visit will be assigned based on the last nominal visit across all procedures and assessments and re-numbered to the last nominal visit number + 1. For example, if a subject attended Visit 1 (Baseline), Visit 2 (Week 4), Visit 3 (Week 8) and then early terminated, the early termination visit will be re-numbered and analyzed as Visit 4 (Week 12).

Unscheduled visits will not be re-numbered and will not be included in OC summaries but will be included in listings. Unscheduled visits will be included in the LOCF imputation by using

target day listed in the Visit Terminology table; for missing visits LOCF values will be based on scheduled and unscheduled visits occurring on or before target day.

8. ANALYSIS SETS

The following subject population will be used for safety and efficacy analyses:

- The intent-to-treat (ITT) population will include all subjects enrolled into the study.

9. STUDY POPULATION

9.1 Subject Disposition

Subject disposition information will be summarized and will include: the number of enrolled subjects, the number of subjects who apply any study medication, the number of subjects who complete the study and who withdraw from the study (together with reasons for withdrawal). The number of subjects whose drug was permanently withdrawn or interrupted due to AE, vIGA-AD™ score or other reasons will also be summarized over the entire study and by visit.

The number of days in the study, defined as the duration between date of study completion / discontinuation (or date of last visit if the study completion/discontinuation date is missing) and the date of Visit 1, will be summarized using descriptive statistics. A figure with Kaplan-Meier curves will also be generated to illustrate this information.

In order to describe the impact of COVID-19 on current study, the following disposition events will be summarized in the tables separately:

- Subjects discontinued from the treatment/study as a result of a positive COVID-19 diagnosis.
- Subjects discontinued from the treatment/study due to other reasons related to COVID-19. This is excluding COVID-19 diagnosis but may include reasons such as site closure, travel restrictions, fear of infection, etc.
- Subjects with study visits altered (including modified in-clinic visit, virtual and phone visits) and missed due to COVID-19.

Previous COVID-19 diagnosis and previous/on-study COVID-19 vaccination, and COVID-19 related protocol deviations will be summarized separately. The impact of COVID-19 (including protocol deviation, visit alteration, treatment/study discontinuation and diagnosis of COVID-19) will also be flagged at subject-level in a data listing. Subject profile will be used to compile all COVID-19 related information for affected subjects.

Also, all COVID-19 related symptoms and confirmed cases that occur during the study will be reported as AEs and included in the summaries.

9.2 Protocol Deviations

Protocol deviations will be summarized by deviation category (major, minor) and will be listed by subject. In addition, COVID-19 related protocol deviations will be summarized separately.

9.3 Eligibility

Subjects not fulfilling any eligibility criteria (i.e., screen failures) will be presented in a data listing. Screen failure reasons for direct-enrolling subjects will be summarized by frequency in a table.

9.4 Demographic and Baseline Characteristics

Demographic variables include age, sex, ethnicity, race, and Fitzpatrick skin type. For subjects rolling over into the OL-LTE study, age will be based on age at time informed consent was signed in the pivotal or maximal use studies. Age for direct-enrolling subjects will be based on age at time informed consent was signed in the OL-LTE study.

Other baseline characteristics include height, weight, body mass index (BMI), vIGA-ADTM, %BSA, EASI score, and PP-NRS.

Medical history

The verbatim term of the medical history condition/event will be coded using the Medical Dictionary for Regulatory Activities (MedDRA), Version 24.0.

Medical history will be summarized descriptively. The summary will show the system organ class (SOC) and preferred terms (PT) sorted alphabetically by SOC followed by descending frequency preferred terms in the Total (Overall) column.

9.5 Prior and Concomitant Medications

Prior and concomitant medication verbatim terms in the eCRFs will be mapped to Anatomical/Therapeutic/Chemical (ATC) class and preferred names using the WHO-Drug Global dictionary (Version B3 01MAR2021).

Prior Medications

For rollover subjects, prior medications are those that were still being used within 30 days before Visit 1 (Baseline), and with a stop date prior to Visit 1. These medications will have been documented in the parent studies, and therefore, will not be presented in this study. For direct-enrolling subjects, prior medications are those that were still being used within 30 days before Screening (Visit 0), and with a stop date prior to first dose of study drug.

For direct-enrolling subjects, it is necessary to exclude previous medications that were stopped more than 30 days prior to Screening. Since the medication stop dates are sometimes partial dates, the following rules for medication stop dates will be used to distinguish between previous medications that will not be summarized (those stopping more than 30 days prior to Screening) and medications that will be summarized as Prior or Concomitant medications.

- If only year was recorded, and it is before the year of Screening Date – 30 days, it is a previous medication that will not be summarized; if year is same or after the year of Screening Date – 30 days, it will be summarized as a Prior or Concomitant Medication.
- If day is missing, but month and year are before those of the Screening Date – 30 days, it is a previous medication that will not be summarized; if month and year are the same as, or after, those of the Screening Date – 30 days, it will be summarized as a Prior or Concomitant Medication.
- If start date is after Screening Date – 30 days, it will be summarized as a Prior or Concomitant Medication.

Prior medications for direct-enrolling subjects will be summarized by WHO ATC class (level 2) and preferred name. The summary will present the number and percentage of subjects using each medication. Subjects may have more than 1 medication per ATC class and preferred name. At each level of summarization, a subject is counted once if he/she reported one or more medications at that level. The summary will be sorted alphabetically by ATC class followed by descending frequency preferred name. Prior medications for direct-enrolling subjects will be listed by subject.

Prior Systemic AD Medications

All systemic (oral and injectable) medications used by the subject for treatment of AD prior to 30 days before the Screening visit will be reported for direct-enrolling subjects. Prior systemic AD medications for direct-enrolling subjects will be summarized by frequency count and percent.

Concomitant Medications

Concomitant medications are those medications that started on or after Visit 1 or medications that started before Visit 1 and continued until on or after baseline (Visit 1) for rollover subjects and continued on or after date of first dose for direct-enrolling subjects. If the medication is ongoing or the stop year is missing, the medication will be considered as received for the entire duration of the study.

To distinguish prior vs concomitant medications for rollover subjects, the following rules for medication stop dates will apply:

- If only year was recorded, and it is before Baseline, it is a prior medication; if year is same or after Baseline, it is assumed to be a concomitant medication.
- If day is missing, but month and year are before Baseline, it is a prior medication; if month and year are the same as Baseline, it is assumed to be a concomitant medication; if month and year are after Baseline, it is a concomitant medication.
- If start date is after Baseline, it is a concomitant medication regardless.

To distinguish prior vs concomitant medications for direct-enrolling subjects, the following rules for medication stop dates will apply:

- If the date of first dose of study drug is missing, it is a prior medication.
- If only year was recorded, and it is before the year of first dose of study drug, it is a prior medication; if year is same or after the year of first dose of study drug, it is assumed to be a concomitant medication.
- If day is missing, but month and year are before the first dose of study drug, it is a prior medication; if month and year are the same as the first dose of study drug, it is assumed to be a concomitant medication; if month and year are after the first dose of study drug, it is a concomitant medication.
- If start date is after the date of first dose of study drug, it is a concomitant medication regardless.

Concomitant medications will be listed by subject. Concomitant medications that are ongoing as of the end of the previous studies will be identified in the same listing.

[figure not shown]
Concomitant medications will be summarized by WHO ATC class and preferred name. Subjects may have more than one concomitant medication per ATC class and preferred name. At each level of summarization, a subject is counted once if he/she reported one or more medications at that level. The summary will be sorted alphabetically by ATC class followed by descending frequency preferred name in the Total (Overall) column.

10. EFFICACY ANALYSES

The efficacy analysis will be based on the ITT population.

10.1 Efficacy Variables

[figure not shown]
Efficacy endpoints

For subjects entering the study with a vIGA-AD™ score ≥ 1 :

- Proportion of subjects who achieve vIGA-AD™=0 at least 1 time on or before Week 48
- [REDACTED]
- [REDACTED]
- [REDACTED]
- [REDACTED]

For subjects entering the study with a vIGA-AD™ score ≥ 2 :

- [REDACTED]
- [REDACTED] change and percent change from Baseline in %BSA affected by visit (OC and LOCF)
- [REDACTED]
- [REDACTED] change and percent change from Baseline in EASI score by visit (OC and LOCF)
- Proportion of subjects with $\geq 50\%$ improvement in EASI score from Baseline by visit (OC and LOCF)
- Proportion of subjects with $\geq 75\%$ improvement in EASI score from Baseline by visit (OC and LOCF)
- Proportion of subjects with $\geq 90\%$ improvement in EASI score from Baseline by visit (OC and LOCF)
- Mean change in average weekly PP-NRS score from Baseline at each study visit (OC and LOCF)
- Proportion of subjects with a Baseline PP-NRS score ≥ 4 who achieve ≥ 4 -point reduction in the average weekly PP-NRS from Baseline at each study visit (OC and LOCF)

- [REDACTED]

10.2 Baseline Values

For subjects rolling over from DMVT-505-3101 or DMVT-505-3102 studies, baseline is defined as the assessment collected at Visit 6 (Week 8) in the pivotal study. If Visit 6 (Week 8) assessment is missing, then Visit 5 (Week 4) will be used as the baseline. If Visit 5 (Week 4) assessment is still missing, the baseline value will be considered as missing. For PP-NRS, baseline is defined as the assessment collected at Visit 6 (Week 8) in the pivotal study. If Visit 6 (Week 8) assessment is missing, then the last PP-NRS at home assessment will be used as the baseline.

For subjects rolling over from DMVT-505-2104 study, baseline is defined as the assessment collected at Visit 4 (Day 28) in the PK study. If Visit 4 (Day 28) assessment is missing, then Visit 3 (Day 8) will be used as the baseline. If Visit 3 (Day 8) assessment is still missing, the baseline value will be considered as missing. [REDACTED]

[REDACTED] For PP-NRS, baseline is defined as the assessment collected at Visit 4 (Day 28) in the PK study. If Visit 4 (Day 28) assessment is missing, then the last PP-NRS at home assessment will be used as the baseline.

For subjects rolling over from DMVT-505-3101, DMVT-505-3102 or DMVT-505-2104 studies, if there are multiple records on the same visit, use the one with later date as the baseline.

For subjects enrolling directly into DMVT-505-3103 study, baseline is defined as the last non-missing value recorded before the first dose of study drug.

Unscheduled visits will not be used in the determination of baseline values.

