PP-NRS (pre-dose) ^p		X	X	X	X	X	X	X	X	X	X	X	X	X	X	
Photograph of disease area ^r				X			X			X			X			

Procedures and Assessment	Long-term Extension Period for All Subjects														FU	ET ^v
	P/C ^w	V 2	V 3	V 4	V 5	V 6	V 7	V 8	V 9	V 10	V 11	V 12	V 13	V 14	NA	
	Week 2	Week 4	Week 8	Week 12	Week 16	Week 20	Week 24	Week 28	Week 32	Week 36	Week 40	Week 44	Week 48	Week 49	NA	
Day 15 (±3 days)	Day 29 (± 3 days)	Day 57 (±3 days)	Day 85 (±3 days)	Day 113 (±3 days)	Day 141 (±3 days)	Day 169 (±3 days)	Day 197 (±3 days)	Day 225 (±3 days)	Day 253 (±3 days)	Day 281 (±3 days)	Day 309 (±3 days)	Day 337 (±3 days)	Day 344 (±3 days)	NA		
Adverse events	X	X	X	X	X	X	X	X	X	X	X	X	X	X	X	X
Concomitant medication	X	X	X	X	X	X	X	X	X	X	X	X	X	X	X	X
Dispense (D) /collect (C) diary ^p		C/D	C/D	C/D	C/D	C/D	C/D	C/D	C/D	C/D	C/D	C/D	C		C	
Review diaries for treatment compliance		X	X	X	X	X	X	X	X	X	X	X	X		X	
Dispense (D) /collect (C) study drug ^s		C/D	C/D	C/D	C/D	C/D	C/D	C/D	C/D	C/D	C/D	C/D	C		C	
Review instructions for study drug application ^t	X	X	X	X	X	X	X	X	X	X	X	X				
Study drug application under supervision ^u		X	X	X	X	X	X	X	X	X	X	X				

a. Baseline Visit to occur at the time of completion of Visit 6 (Week 8) from the DMVT-505-3101 or DMVT-505-3102 studies. Assessments with an unbracketed X should be completed at the Baseline visit. For assessments with a bracketed X, the assessment completed at the final visit of the parent study will be used as the Baseline value for this study.

b. Baseline Visit to occur at the time of completion of Visit 4 (Day 28) from the DMVT-505-2104 study. Assessments with an unbracketed X should be completed at the Baseline visit. For assessments with a bracketed X, the assessment completed at the final visit of the parent study will be used as the Baseline value for this study.

c. Demographics/Fitzpatrick skin type as collected at Screening in one of three parent studies (Phase 3 pivotal safety and efficacy study DMVT-505-3101, Phase 3 pivotal safety and efficacy study DMVT-505-3102, or Phase 2 maximal use PK study DMVT-505-2104).

d. Review medical history as collected in one of three parent studies.

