7.2 Visit 1; Baseline (Day 1)

7.2.1 Baseline Visit for Subjects Rolling Over from DMVT-505-3101 and DMVT-505-3102

On Day 1, subjects from the parent studies DMVT-505-3101 or DMVT-505-3102 who were considered eligible for this study will sign the ICF and be reassessed to confirm eligibility to participate in this study. All subjects who continue to meet study eligibility criteria will be enrolled. Subjects entering with a vIGA-AD™ ≥ 1 will receive treatment with tapinarof cream, 1% until they achieve a vIGA-AD™ score of 0, at which time treatment will be discontinued and subjects monitored for maintenance of the remittive effect. If/when

disease worsening occurs, as evidenced by a vIGA-AD™ ≥ 2 , treatment will then be re-initiated and continued until a vIGA-AD™ of 0 is observed. Subjects entering with a vIGA-AD™ of 0 will have treatment discontinued beginning at the Baseline visit and will be monitored for maintenance of the remittive effect.

The following procedures and assessments will be performed at the Baseline visit:

- Demographics and Fitzpatrick skin type (carried over from parent study)
- Medical history (carried over from parent study)
- Brief physical exam (last assessment from parent study)
- Vital signs measurements (last assessment from parent study)
- Urine pregnancy test (WOCBP; last assessment from parent study)
- Blood sample collection for clinical laboratory tests (serum chemistry and hematology; last assessment from parent study)
- Urinalysis (last assessment from parent study)
- vIGA-AD™ score (excluding subject's scalp; last assessment from parent study)
- %BSA affected calculation (excluding subject's scalp; last assessment from parent study)
- EASI (excluding subject's scalp; last assessment from parent study)
- [REDACTED]
- [REDACTED]
- [REDACTED]
- PP-NRS (last assessment from parent study)
- [REDACTED]
- [REDACTED]
- [REDACTED]
- Photography of a representative area of the subject's disease area (at a subset of study sites only; last photograph from parent study)
- AE recording (ongoing from parent study at the time the ICF is signed in this study)
- Concomitant medication recording (ongoing from parent study at the time the ICF is signed in this study)
- Dispense diary (subjects or their caregivers will be instructed in how and when to complete diary)
- Dispense study drug, if applicable
- Instruction on how to apply study drug, if applicable
- Study drug application under supervision, if applicable

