7.2.3 Baseline Visit for Subjects Enrolling Directly into DMVT-505-3103

On Day 1, subjects will be reassessed to confirm continued eligibility to participate in the study. All subjects who continue to meet study eligibility criteria will be randomized to treatment.

The following additional procedures and assessments will be performed at the Baseline Visit:

- Changes to medical history will be recorded
- Brief physical examination
- Vital signs measurement
- Urine pregnancy test (WOCBP)

- Blood sample collection for clinical laboratory tests (serum chemistry and hematology)
NOTE: Blood sample collection for clinical laboratory tests is not required at the Baseline Visit if it has been \leq 14 days since samples were collected at Screening and the results of those clinical laboratory tests were within the normal range.
- Urinalysis
NOTE: Urine sample collection for urinalysis is not required at the Baseline Visit if it has been \leq 14 days since samples were collected at Screening and the results of those analyses were within the normal range.
- vIGA-AD™ score (excluding subject's scalp)
- %BSA affected calculation (excluding subject's scalp)
- EASI (excluding subject's scalp)
- [REDACTED]
- [REDACTED]
- [REDACTED]
- PP-NRS (by subject or caregiver)
- [REDACTED]
- [REDACTED]
- [REDACTED]
- Photography of a representative area of the subject's disease area (at a subset of study sites only)
- AE recording
- Concomitant medication recording
- Dispense diary (subjects or their caregivers will be instructed on how and when to complete diary)
- Dispense study drug
- Instruction on how to apply study drug
- Study drug application under supervision

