10.4 Handling of Dropouts or Missing Data

Efficacy endpoints will be summarized by visit using OC. Additionally, efficacy endpoints will be summarized by visit using LOCF to impute missing data. LOCF will include scheduled and unscheduled visits. Baseline values will not be carried forward.

Average weekly PP-NRS scores will be calculated for all nominal visits as the average of 7 daily post-baseline PP-NRS scores prior to and including the values assessed on the visit date. If daily PP-NRS scores are missing for more than 3 days in a 7-day period, the average weekly PP-NRS score will be set to missing. If two or more scores are reported on the same day, the maximum score on that day will be used.

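### One day's itch score both selects subjects (≥4) and anchors the ≥4-point PP-NRS response, so regression to the mean can inflate the rate when true improvement is small to moderate

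*SAP*

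**What the plan says.** For rollovers from the two pivotal studies, SAP 10.2 states: "For PP-NRS, baseline is defined as the assessment collected at Visit 6 (Week 8) in the pivotal study". If that assessment is missing, "then the last PP-NRS at home assessment will be used as the baseline", which is again one score. Rollovers from the maximal use study are handled the same way at Day 28. For direct-enrolling subjects, "baseline is defined as the last non-missing value recorded before the first dose of study drug".

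The responder endpoint in SAP 10.1 is restricted to subjects whose Baseline PP-NRS is at least 4. It counts those with at least a 4-point "reduction in the average weekly PP-NRS from Baseline at each study visit". Under SAP 10.4 the follow-up value is the mean of 7 daily scores, set to missing "If daily PP-NRS scores are missing for more than 3 days in a 7-day period". That averaging applies only after baseline.

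The single baseline comes from the protocol for rollovers. Table 1, notes a and b, say that for bracketed items "the assessment completed at the final visit of the parent study will be used as the Baseline value for this study", and sections 7.2.1 and 7.2.2 list "PP-NRS (last assessment from parent study)". The protocol's own responder endpoint (Synopsis and section 10.4.2) refers to PP-NRS without a weekly average, yet SAP 14 declares no changes to the protocol-specified analyses.

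**The concern.** Protocol Appendix 13 asks for the worst itch in the previous 24 hours, so one score describes one day. A subject whose usual itch is below 4 can enter the denominator on a bad day. For any subject, a bad baseline day also makes the later 7-day mean look like a larger fall. The plan smooths daily noise after baseline but leaves it in at the one point where it both selects and anchors.

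Every subject may receive tapinarof and there is no comparator, so chance responders cannot be removed by difference. SAP 10.3 plans no covariate adjustment. What is at stake is an overstated itch response rate. SAP 6 rules out statistical testing, so no error rate is affected.

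**Working it through.** **No plan figure to reproduce.** The documents give no expected response rate, PP-NRS mean, SD or day-to-day correlation. Everything below is therefore an assumed range.

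**Taken from the documents:** 0 to 10 scale with 24-hour recall (Protocol Appendix 13); single-score baseline (SAP 10.2); selection at ≥4 and response at a fall of ≥4 (SAP 10.1); 7-day mean at follow-up (SAP 10.4).

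**Assumed:** between-subject SD 2; daily SD 1, 1.5 or 2; mean itch 3 or 5; first-order autocorrelation between days of 0, 0.5 or 0.8; true improvement normally distributed.

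**Mechanism.** Ignoring rounding and scale limits, a subject with baseline value y has expected true level μ + R(y − μ), where R = between-subject variance / (between-subject variance + error variance of the baseline). Take μ = 3, y = 6, daily SD 2:

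- Single score: R = 4/(4 + 4) = 0.50. The expected true level is 4.5, so a fall of 1.5 is expected with no treatment effect.
- 7-day mean, independent days: error variance 4/7 = 0.57, R = 4/4.57 = 0.875, expected fall 3 × 0.125 = 0.38.
- 7-day mean, autocorrelation 0.8: the error variance is multiplied by [7 + 2Σ(7 − k)0.8^k]/49 = 31.39/49 = 0.64, giving 2.56. Then R = 4/6.56 = 0.61 and the expected fall is 3 × 0.39 = 1.17.

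Averaging therefore helps a great deal if days are nearly independent and little if they are strongly correlated.

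**Response rates by simulation** (300,000 subjects per cell; scores rounded and limited to 0–10; true mean improvement 2, SD 2). *Single* applies the SAP rule. *Weekly* uses a 7-day baseline mean for both selection and change. *Noise-free* applies both thresholds to the underlying levels and gives about 16%. Differences are in percentage points.

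| Autocorrelation | Single − weekly | Single − noise-free | Weekly − noise-free | Share of bias removed by weekly |
|---|---|---|---|---|
| 0.8 | 0.9 to 2.5 | 6.5 to 21.5 | 5.6 to 19.0 | 11–16% |
| 0.5 | 2.3 to 8.5 | 5.3 to 18.2 | 3.1 to 9.7 | 42–48% |
| 0 | 3.3 to 15.5 | 4.3 to 16.4 | 0.7 to 1.2 | 77–94% |

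With between-subject SD 1.5 or 2.5, the single-minus-weekly gap is 0.8–2.5, 2.2–9.1 and 3.3–17.2 for autocorrelation 0.8, 0.5 and 0.

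**No true change**, single versus weekly: 0.2–11.1% versus 0.0–7.5% (autocorrelation 0.8), 0.1–8.1% versus 0.0–1.3% (0.5), 0.0–6.2% versus 0.0% (0).

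**Large improvements.** At improvement 4 (SD 2) the gap is −0.2 to +0.4, 0.5 to 5.8 and 1.3 to 12.5 for autocorrelation 0.8, 0.5 and 0. At improvement 5 (SD 1, daily SD 1, mean itch 3–6) it is −5.7 to −1.8.

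**Selection or anchor?** A separate simulation used autocorrelation 0.3, improvement SD 1.5 and mean itch 3 to 6.5. It gave single-minus-weekly gaps of +1.0 to +14.9 points for improvements of 0 to 3, and −1.7 to +5.1 at 5. In one of its cells (mean itch 5, daily SD 1.5, improvement 2):

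- both roles on the single score: 21.5%;
- weekly selection, single-score anchor: 19.3%;
- single-score selection, weekly anchor: 12.1%;
- both roles weekly: 13.6%.

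Here the anchor contributes most, and single-score selection adds 21.5 − 19.3 = 2.2 points on top. Changing selection alone would leave most of the excess, so both roles must change together.

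**Mean change.** Without the ≥4 restriction, the two baselines differ by at most 0.01 points.

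**Diary completeness.** If the visit-day score is present, at least 3 of 6 home days are needed to reach 4 of 7. With each home day missing at random, 1 − (0.3⁶ + 6·0.7·0.3⁵ + 15·0.7²·0.3⁴) = 93% qualify at 30% missing, and 42/64 = 66% at 50% missing. At 30% missing the improvement-2 gap is 1.7–3.3, 3.0–9.4 and 3.8–15.0 for autocorrelation 0.8, 0.5 and 0.

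**The case against.** The plan makes no mistake here. For rollovers the single baseline is what the protocol specifies, SAP 10.2 applies it consistently, and this is one of many untested summaries. The size rests wholly on assumptions, and for large effects even the sign is open. The largest gaps need nearly independent days, which nothing in the documents supports for a chronic disease. The weekly baseline still uses one quantity for both roles, removes only 11–16% of the bias at autocorrelation 0.8, and cannot be built for direct-enrolling subjects. A second table could reassure too much. Parts of SAP 10.1, 10.2 and 11.1 are blacked out, so a weekly baseline may already exist. The weekly averaging at follow-up can also be read as detail that the protocol leaves to the SAP.

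Much of this stands, and it limits the point to a modest improvement. It does not remove the mechanism: the pivotal PP-NRS baseline sentence is fully readable, and nothing readable corrects or discloses the effect. Where days are strongly correlated the weekly table gains little, but the total bias remains large, so the footnote is needed whichever correlation applies. Small-to-moderate change is also plausible, because a rollover subject's Baseline is the end of parent-study treatment. That is an inference, since the documents give no itch data.

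**Conclusion.** The concern holds as a low-cost improvement in method. In a study with no control arm, the ≥4-point PP-NRS responder proportion can be overstated when true improvement is small to moderate. At a true improvement of 2 points, the excess over the noise-free rate is 4.3 to 21.5 percentage points under the assumed SDs and correlations. Of this, a weekly baseline would remove between about a tenth and nine tenths, depending on how strongly successive days are correlated. For improvements of about 4 points or more, the gap between the two baselines may be negligible or reversed. Mean change in PP-NRS is essentially unaffected. Confidence in the direction, within that range of improvement, is good. The size in this trial cannot be fixed from the documents.

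**What to change.** For the ≥4-point responder endpoint only, add an analysis for rollover subjects to SAP 10.1 and 10.2:

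- Define Baseline PP-NRS as the mean of the parent-study daily scores over the 7 days up to and including Visit 1. Apply the SAP 10.4 rules: at least 4 of 7 days, and the maximum if a day has more than one score.
- Use that mean for both the ≥4 selection and the change.
- Report it by visit beside the protocol's single-assessment result in the rollover columns, with each denominator.
- Keep the single-assessment baseline for mean change, for the overall column and for direct-enrolling subjects. Their Visit 1 procedures include "Dispense diary (subjects or their caregivers will be instructed on how and when to complete diary)", so they have no earlier diary.
- Footnote the single-assessment responder table: one score selects subjects and anchors the change, regression to the mean may raise the proportion, and there is no control arm.
- List the weekly averaging and the added analysis in SAP 14.

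The cost is one table, one footnote and two SAP 14 entries, with no new data collection. SAP 10.2 already relies on parent-study home scores, but the documents do not show how often they were collected or how complete they are. The added rate may be less favourable, does not cover direct-enrolling subjects, and should not be presented as free of bias.
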